Appendix C. Study Activities – Treatment Period

Activity	Screening	Day 1^a	Wk 4	Wk 8 (Arm B Only)	EOT (Arm A and Arm B) or Premature D/C from Treatment^b
Informed Consent ^c	X				
Dispense/Review Study Drug Dosing Card	X	X (Dispense only)	X	X	X (Review only)
Medical History ^d	X	X			
Physical Exam ^e	X	X			X
Vital Signs, Weight, Height ^f	X	X	X	X	X
ECG	X				
Hematology/Chemistry ^g /Coagulation Panel	X	X	X	X	X
Pregnancy Test (serum [s] urine [u]) ^h	X (s)	X (u, s)	X (u)	X (u)	X (u)
Anti-HCV Ab, Anti-HIV Ab	X				
Hepatitis B Panel	X				
HCV Genotype and Subgenotype	X				
FibroTest or FibroScan [®] or Liver Biopsy ^j	X				
Concomitant Medication Assessment	X	X	X	X	X
Adverse Event Assessment ^k	X	X	X	X	X
Study Drug Dispensed		X	X	X ^k	
HCV RNA Samples	X	X	X	X	X
Study Drug Accountability and Review of Study Drug Adherence			X	X	X ^l
HCV Resistance Sample		X	X	X	X

Activity	Screening	Day 1 ^a	Wk 4	Wk 8 (Arm B Only)	EOT (Arm A and Arm B) or Premature D/C from Treatment ^b
Pharmacokinetic Samples ^m			X	X	X
Child-Pugh Score (subjects with compensated cirrhosis only)	X	X			X
Clinical Assessment of Hepatic Decompensation (subjects with compensated cirrhosis only)		X			
HCC Screening Liver ultrasound (subjects with compensated cirrhosis only)	X				
Patient Reported Outcomes Instruments (PROs) ⁿ		X			X
Flow cytometry sample ^o	X	X	X	X	X
HIV RNA ^o	X	X	X	X	X

Wk = Week; EOT = End of treatment; D/C = Discontinuation

* The EOT visit can be at Week 8 or 12 in accordance with treatment duration as described in Section 5.1.

- All procedures to be performed prior to first dose.
- Subjects who prematurely discontinue during the Treatment Period should return to the site to complete the Premature D/C Visit Procedures (preferably prior to the initiation of any other anti-HCV therapy).
- Subjects need to sign an IRB/IEC approved informed consent for the study (prior to performing any Screening or study-specific procedures).
- A complete medical history will be taken at Screening and will be updated at the Study Day 1 Visit.
- A symptom-directed physical examination may be performed at any other visit, when necessary. Any significant physical examination findings after the first dose will be recorded as adverse events.
- Height will be measured at the Screening Visit only.
- Blood samples for serum chemistry tests should be collected following a minimum 8-hour fast prior to study drug intake (with the exception of the Screening Visit, which may be non-fasting).
- Pregnancy testing is not required for women not of childbearing potential as defined in Section 5.2.4.

- i. For subjects who have not had a qualifying liver biopsy within the previous 24 months for subjects without cirrhosis or at any time for subjects with compensated cirrhosis) or a qualifying FibroScan® within the previous 6 months for subjects without cirrhosis or at any time prior to Screening for subjects with compensated cirrhosis).
- j. Subjects with a historical negative Liver Ultrasound, CT or MRI (within 3 months prior to screening) are not required to have a screening Liver Ultrasound performed. If additional Liver Ultrasound testing is required it should be completed as an unscheduled visit. A positive ultrasound result suspicious of HCC will be confirmed with CT scan or MRI. A liver ultrasound should be performed at the end of treatment visit if it has been 6 months or more since the historical evaluation.
- k. See specific information regarding adverse event collection in Section [6.1.1.1](#).
- l. Dispensation at Week 8 and Study Drug Accountability at Week 12 are only applicable to Arm B. Subjects should bring all study drug to every visit for the site to review adherence. However, the site will record the number of tablets returned only at the Study Drug Accountability Visits at Weeks 4, 8, 12 (if applicable) or Premature D/C.
- m. PK samples will be collected at each scheduled study visit. Detail regarding timing of samples is provided in Section [5.3.2.1](#).
- n. PROs should be administered before any study procedures in the order listed in Section [5.3.1.1](#).
- o. For HCV/HIV co-infected subjects.

Appendix D. Study Activities – Post-Treatment (PT) Period

Activity	PT Wk 4	PT Wk 12	PT D/C ^a
Vital Signs and Weight	X	X	X
Hematology/Chemistry/Coagulation Panel	X		X ^b
Pregnancy Test (urine) ^c	X (u)		X (u) ^b
Concomitant Medication Assessment ^d	X	X ^d	X ^d
Child-Pugh Score (subjects with compensated cirrhosis only)		X	X
Adverse Event Assessment ^e	X ^e	X ^f	X ^f
HCV RNA Samples	X	X	X
HCV Resistance Sample	X	X	X
Patient Reported Outcomes Instruments (PROs) ^g		X	X
Flow cytometry sample ^h	X	X	
HIV RNA ^h	X	X	

Wk = Week; PT D/C = Post-Treatment Discontinuation

- Subjects who prematurely discontinue from the Post-Treatment Period should return to the site to complete the PT D/C Visit procedures.
- Hematology/Chemistry/Coagulation Panel and Pregnancy Test are not required at PT Wk 12, but only at PT D/C if subject discontinues prior to PT Wk 4.
- Women of childbearing potential do not require pregnancy testing beyond PTW4. Pregnancy testing will be performed at PT D/C visit only if the subject discontinues prior to PTW4. Pregnancy testing in PT Period is not required for females of non-childbearing potential as defined in Section 5.2.4.
- Only medications taken for SAEs and treatment of HCV will be collected after 30 days post-dosing.
- Nonserious AEs and all SAEs will be collected until 30 days post dosing. All spontaneously reported SAEs will be collected thereafter. See specific information regarding adverse event collection in Section 6.1.4.

- f. Only SAEs will be collected thereafter as described in Section [6.1.4](#).
- g. PROs should be administered before any study procedures in the order listed in Section [5.3.1.1](#).
- h. For HCV/HIV co-infected subjects.

Note: Day 1 of the Post-Treatment Period will be defined as the day after the last dose of study drug.

16.1__9 Documentation of Statistical Methods

16.1__9.1 Statistical Analysis Plan

3.0 Introduction

This statistical analysis plan (SAP) describes the statistical analyses to be completed by the AbbVie Statistics and Statistical Programming Departments for Study M16-156. Study M16-156 evaluates the efficacy and safety of GLE/PIB in treatment-naïve adults in Brazil with chronic hepatitis C virus (HCV) genotype (GT) 1 – 6 infection without cirrhosis (fibrosis stage of F2 – F3) for an 8-week treatment duration or with compensated cirrhosis (fibrosis stage F4) for a 12-week treatment duration.

This SAP (Version 1.0) provides details to further elaborate the statistical methods outlined in Clinical Study Protocol M16-156 incorporating Amendment 1 and 2 dated 02 August 2018, and describes analysis conventions to guide the statistical programming. Analyses will be performed using SAS[®] Version 9.4 (SAS Institute, Inc., Cary, NC 27513) or later under the UNIX operating system.

4.0 Study Objectives, Design and Procedures

4.1 Objectives

The primary objectives of this study are to assess the efficacy by evaluating the percentage of subjects achieving SVR₁₂ (HCV RNA < LLOQ 12 weeks following therapy) and safety of GLE/PIB combination in treatment-naïve adults in Brazil with chronic hepatitis C virus (HCV) genotype (GT) 1 – 6 infection without cirrhosis or with compensated cirrhosis. The efficacy and safety endpoints will be analyzed on the overall population (i.e., across treatment durations and genotypes).

The secondary objectives are to assess efficacy of GLE/PIB based on overall population (i.e., across treatment durations and genotypes) by evaluating the following:

- The percentages of subjects with HCV on-treatment virologic failure (OTVF);
- The percentages of subjects with HCV virologic relapse.

4.2 Design Diagram

[figure not shown]
This is a Phase 3b, open-label, multicenter study to evaluate the efficacy and safety of GLE/PIB for an 8- or 12-week treatment duration in adults in Brazil with chronic HCV GT1 – 6 infection, without cirrhosis or with compensated cirrhosis with a METAVIR System Fibrosis Score of F2, F3 or F4 (F2 - F4) or equivalent, who are HCV treatment-naïve. Approximately 100 subjects meeting the eligibility criteria will be enrolled. The study enrollment will be monitored to meet the following enrollment criteria: 1) a minimum of approximately 35 GT1 and 25 GT3 subjects and 2) approximately 80 F2 – 3 and a maximum of approximately 20 F4 subjects.

Subjects will be enrolled into one of the following treatment arms:

- Arm A: HCV GT 1 – 6 without cirrhosis (F2 – F3) subjects will be treated with GLE/PIB 300 mg/120 mg once daily (QD) for 8 weeks.
- Arm B: HCV GT 1 – 6 subjects with compensated cirrhosis (F4) will be treated with GLE/PIB 300 mg/120 mg once daily (QD) for 12 weeks.

A study schematic is shown below in [Figure 1](#).

Figure 1. Study Design

4.3 Sample Size

It is anticipated that a total of approximately 100 HCV infected treatment naïve GT1 – 6 subjects will be enrolled in this study. No formal hypothesis is being tested. If

the observed SVR₁₂ rate in this study is 97% among 100 HCV GT1 – 6 treatment naive subjects, then the half-width of 2-sided 95% normal approximation to the binomial distribution confidence interval will be 3.3% (EAST 6.4).

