8.0 Statistical Methods and Determination of Sample Size

8.1 Statistical and Analytical Plans

An interim data lock may occur in the study if interim study results are needed for regulatory interaction purposes. No changes to the study design or treatment of subjects would result from this interim analysis; therefore, no adjustment for multiplicity is needed.

SAS® (SAS Institute, Inc., Cary, NC) for the UNIX operating system will be used for all analyses. All confidence intervals will be two-sided with an alpha level of 0.05.

Descriptive statistics will be provided, such as the number of observations (N), mean, and standard deviation (SD) for continuous variables and counts and percentages for discrete variables.

Safety and demographic analyses will be performed on all subjects who receive at least one dose of study drug.

Efficacy analyses will be performed on the intention-to-treat (ITT) population defined as all enrolled subjects who receive at least one dose of study drug, unless otherwise specified.

Sensitivity analyses of the primary efficacy endpoint, when applicable, will be performed on the intention-to-treat population modified to exclude subjects who did not achieve SVR₁₂ for reasons other than virologic failure (mITT-VF).

No data will be imputed for any efficacy or safety analysis except for analyses of SVR endpoints (HCV RNA data). HCV RNA values will be selected for the analyses of all SVR endpoints (e.g., SVR₄ and SVR₁₂) based on defined visit windows. A backward imputation method will be used to impute missing responses for SVR analyses.

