8.1.2.1 Primary Efficacy Endpoints

The primary efficacy endpoint is the percentage of subjects who achieve SVR₁₂ (HCV RNA < LLOQ 12 weeks after the last actual dose of study drug) across all genotypes (GT1 – 6 subjects) will be analyzed on combined treatment groups. The primary endpoint will be analyzed based on intention to treat (ITT) population. The number and percentage of subjects achieving SVR₁₂ will be summarized with a two-sided 95% confidence interval using the normal approximation to the binomial distribution, unless the number of SVR₁₂ non-responders is less than 5, in which case the Wilson's score method will be used for the confidence interval instead.

A summary of reason for SVR₁₂ non-response (e.g., OTVF, relapse, other) will be provided.

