8.2 Determination of Sample Size

It is anticipated that a total of approximately 100 HCV infected treatment naïve GT1 – 6 subjects will be enrolled in this study. No formal hypothesis is being tested. If the observed SVR₁₂ rate in this study is 97% among 100 HCV GT1 – 6 treatment naive subjects, then the half-width of 2-sided 95% normal approximation interval is 3.3%.

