- Update Section 1.2, Synopsis, Section 5.3.1.1, Study Procedures, Patient Reported Outcomes (PRO) Instruments (Questionnaires), [Appendix C](#), Study Activities – Treatment Period

Rationale: *Removed the administration of the Treatment Satisfaction Questionnaire from the Day 1 study visit.*

- Update Section 6.1.7.1, Management of Increases in ALT

Rationale: *Updated the section by deleting anti-hepatitis A virus immunoglobulin test and replacing it with anti-hepatitis A virus total test as a result of an error in the original list of tests.*

- Update Section 7.0, Protocol Deviations

Rationale: *Updated contact information*

- Update Section 8.1.1, Demographics and Baseline Characteristics

Rationale: *To remove one of the baseline characteristics from the summary of subjects as it was not applicable for this study.*

- Update Synopsis and Section 8.1.2.1, Primary Efficacy Endpoints
Rationale: *For high SVR₁₂ rates, that are nonetheless less than 100%, the normal approximation to binomial distribution does not provide good coverage. Thus, the Wilson score test will be used for calculating the 95% confidence interval in the primary efficacy analysis, rather than using the normal approximation to the binomial distribution, if the number of SVR₁₂ non-responders is less than 5; otherwise, the normal approximation to the binomial distribution will be used.*
- Update Synopsis and Section 8.1.3, Patient Reported Outcomes
Rationale: *To remove mean change from baseline calculation for TSQM Effectiveness, Side Effects, Convenience, and Global Satisfaction scores. The Treatment Satisfaction Questionnaire (TSQM) is to measure the satisfaction of a treatment. At Day 1 prior to dosing, the subject has not received any study medication.*
- Update Synopsis and Section 8.1.2.5, Additional Efficacy Endpoints
Rationale: *To remove the endpoint of the percentage of subjects with relapse after SVR₁₂ as this information will not be collected.*
- Update Section 6.2.2, Reporting, Section 9.1, Independent Ethics Committee (IEC) or Institutional Review Board (IRB), Section 10.1, Source Documents, and Section 13.0, Completion of the Study.
Rationale: *Language was updated, per the latest AbbVie protocol template.*
- Update Appendix B, List of Protocol Signatories
Rationale: *Updated to reflect changes in signatories.*
- Update Appendix D, Study Activities – Post-Treatment (PT) Period

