10.3 Primary Efficacy Analysis

The primary efficacy endpoint is the percentage of subjects who achieve SVR₁₂ (HCV RNA < LLOQ 12 weeks after the last actual dose of study drug) based on the overall ITT population. The number and percentage of subjects achieving SVR₁₂ will be calculated along with a two-sided 95% CI using the normal approximation to the binomial distribution, unless the number of SVR₁₂ non-responders is less than 5, where the Wilson's score method¹ will be used to calculate the CI instead.

A summary of the reasons for SVR₁₂ non-response (e.g., on-treatment virologic failure, relapse, other) will be provided. A listing of subjects who do not achieve SVR₁₂ by reason for non-response will also be provided.

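### The only stated precision for N = 100 (half-width 3.3% at 97/100) belongs to a normal-approximation interval, but the plan's own rule makes Wilson (91.5% to 99.0%) the primary interval at that result

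*SAP*

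**What the plan says.** Both documents describe the size of the trial by precision alone and state that no formal hypothesis is tested. SAP 4.3 expects that "a total of approximately 100 HCV infected treatment naïve GT1 – 6 subjects will be enrolled in this study". It takes as its scenario that "the observed SVR₁₂ rate in this study is 97% among 100 HCV GT1 – 6 treatment naive subjects", and concludes "then the half-width of 2-sided 95% normal approximation to the binomial distribution confidence interval will be 3.3% (EAST 6.4"). Protocol 8.2 uses the same scenario: "then the half-width of 2-sided 95% normal approximation interval is 3.3"%. Neither document gives any other precision figure for N = 100. Protocol 5.1 adds only general scientific, regulatory and ethical reasons for enrolling about 100.

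The interval for the primary endpoint is set elsewhere. SAP 10.3 uses the normal approximation unless the number of SVR12 "non-responders is less than 5, where the Wilson's score method" applies. Protocol 8.1.2.1 has the same threshold, "in which case the Wilson's score method will be used for the confidence interval instead". SAP 10.5 and protocol 8.1.2.3 add a Wilson interval for ITT SVR12 as a sensitivity analysis, whatever the count.

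**The concern.** The scenario in the sample-size sentence has 3 non-responders, which is below the threshold of 5. At that result the primary interval is Wilson and the ITT sensitivity interval is also Wilson. The plan specifies no normal-approximation interval for the overall ITT SVR12 rate there, so the 3.3% describes an interval that would not be produced for it.

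The sponsor has already given the reason for preferring Wilson. The Amendment 1 rationale for changing protocol 8.1.2.1 says that for high SVR12 rates below 100% "the normal approximation to binomial distribution does not provide good coverage". The interval rule was changed at that point and the sample-size sentence was left as it was. This history explains the mismatch. The defect itself lies between sections of the current documents.

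With no hypothesis test, this figure is the only quantitative statement of what 100 subjects will deliver. A reader would take it as about 3.3 points either side of 97%. The planned interval is wider and asymmetric, and most of the extra uncertainty is on the low side, which matters most for a high cure rate.

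**Working it through.** **Inputs.** N = 100 and an observed rate of 97% (SAP 4.3, protocol 8.2). Two-sided intervals with alpha 0.05 (protocol 8.1), so z = 1.96. Wilson if there are fewer than 5 non-responders, otherwise the normal approximation (SAP 10.3, protocol 8.1.2.1). Missing SVR12 data count as failure after the imputation steps (SAP 6.3), so the denominator stays at the ITT N.

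**1. The plan's own figure.** Normal half-width = z × √(p(1 − p)/n) = 1.96 × √(0.97 × 0.03/100) = 3.34 points, which reproduces the stated 3.3%. The interval is 93.66% to 100.34% before truncation, so its upper limit exceeds 100%.

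**2. Which interval the rule selects.** Non-responders = 100 − 97 = 3, fewer than 5, so Wilson. At N = 100 Wilson is primary for 96 to 100 responders.

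**3. The Wilson interval at 97/100.**
- Centre = (p + z²/2n)/(1 + z²/n) = (0.97 + 0.0192)/1.0384 = 95.26%.
- Half-length = z × √(p(1 − p)/n + z²/4n²)/(1 + z²/n) = 1.96 × √(0.000291 + 0.000096)/1.0384 = 3.71 points.
- Limits: 91.55% to 98.97%, that is 5.45 points below 97% and 1.97 above.

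| At 97/100 | Lower | Upper | Half-length |
|---|---|---|---|
| Normal (stated) | 93.66% | 100.34% | 3.34 |
| Wilson (planned) | 91.55% | 98.97% | 3.71 |

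The half-length differs by 3.71 − 3.34 = 0.37 points and the lower limit by 93.66 − 91.55 = 2.11 points.

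**4. Where the normal approximation first applies.** With 5 non-responders, 95/100: 1.96 × √(0.95 × 0.05/100) = 4.27 points (90.73% to 99.27%). For any SVR12 from 5% to 95% the normal half-width at N = 100 is at least this, so over that range a primary normal interval as narrow as 3.3 points cannot arise.

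**5. How often the rule selects Wilson.** Assume a true SVR12 of 97%. The binomial probability of 4 or fewer non-responders is 0.818 at N = 100. Because the plan says approximately 100, the range is 0.843 at N = 95 to 0.792 at N = 105.

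**6. Exact coverage at a true 97%, N = 100.** The normal interval used at every count covers 97% with probability 0.802. It misses at 99/100 (97.05% to 100.95%, probability 0.147), at 100/100 (zero width, 0.048) and at 91 or fewer responders (0.003). Wilson used at every count covers with probability 0.969. The planned rule, which switches between the two, covers with probability 0.997.

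**The case against.** The strongest reply is that the two statements do not contradict each other. SAP 4.3 says what a normal-approximation half-width would be at 97%, names the method and is correct. SAP 10.3 says which interval will be reported. Nobody programming the analysis would be misled, no target width is stated from which N was derived, and there is no threshold that a 2-point shift in the lower limit could cross. The poor coverage of the normal interval arises almost entirely at 99 and 100 responders, where the rule already uses Wilson, and the planned rule does not undercover at a true 97%. Finally, SAP 12.1 reports that no HIV co-infected subjects enrolled. Recruitment was therefore probably complete or nearly so when the SAP was written, and a forward-looking precision sentence informs little that remains.

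Much of this stands. There is no effect on N, conduct or the reported result, and the 80.2% coverage is a reason not to quote the normal interval, not a fault in the planned analysis. What does not stand is that the sentence is adequate as an illustration. It is the only one given, and it shows an interval that the plan would not report for overall ITT SVR12 in its own scenario. Naming the method does not make it the planned interval.

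**Conclusion.** The concern holds. The 3.3% is correctly computed for the interval it names, but it is not the precision of the planned primary interval at 97/100. That interval is Wilson, 91.5% to 99.0%. The understatement is 0.37 points in half-length and 2.1 points at the lower limit.

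The interval comparison rests only on the plan's own scenario of 97 of 100 and its own switching rule. The selection probability of about 82% and the coverage figures rest in addition on an assumed true SVR12 of 97%. The sentence should be corrected, but the consequence is limited to the planning text: no decision rule, sample size or reported analysis depends on it.

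**What to change.** In SAP 4.3 and protocol 8.2, replace the half-width statement with the limits, for example: *with 97 of 100 subjects achieving SVR12, the two-sided 95% Wilson score interval is 91.5% to 99.0%*. Give the limits and not a plus-or-minus figure, because the interval is centred on 95.3%, not 97%, and 3.7 points either side of the estimate would be wrong.

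The cost is one sentence in each document and a slightly less favourable stated precision. N, conduct and the reported analysis do not change. If no protocol amendment is otherwise planned, changing the SAP sentence alone is sufficient.

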4.4 Planned Analyses

All analyses will be conducted by statisticians and programmers at AbbVie or designees according to the methodologies specified in this SAP.

An interim data lock may occur in the study if interim study results are needed for regulatory interaction purposes. No changes to the study design or treatment of subjects would result from this interim analysis; therefore, no adjustment for multiplicity is needed.

The end-of-study analysis will be conducted when all subjects enrolled in the study have completed the Post-Treatment Week 12 Visit or prematurely discontinued from the study. Data will be locked after performing appropriate data cleaning. Results from this analysis (e.g., SVR₁₂ data) will be described in the final clinical study report (CSR).

5.0 Analysis Populations

5.1 Definitions of Analysis Populations

5.1.1 Intention-to-Treat (ITT) Population

All subjects who receive at least one dose of study drug will be included in the ITT population. Demographic, baseline characteristic, exposure, concomitant medication and medical history analyses will be performed on the ITT population overall and according to the treatment assignment, i.e., subject grouping will be based on the arm to which the subject was assigned. Efficacy analyses will be performed on the overall ITT population, combining Arm A and Arm B which administer the recommended duration of GLE/PIB per labelling.

